7.1.6. Summaries of Adverse Events and Deaths

Treatment-emergent AEs will be summarized based on the Safety Analysis Set.

7.1.6.1. Summaries of AE incidence in Combined Severity Grade Subsets

The number and percentage of subjects who experienced at least 1 TEAE will be provided and summarized by SOC, HLT, PT, and treatment group. For other AEs described below, summaries will be provided by SOC, PT, and treatment group:

- TEAE by maximum severity
- TEAEs of Grade 3 or higher (by maximum severity)
- TEAEs of Grade 2 or higher
- All TE treatment-related AEs
- All TE treatment-related AEs (by maximum severity)
- TE Treatment-related AEs of Grade 3 or higher (by maximum severity)
- TE Treatment-related AEs of Grade 2 or higher
- All TE SAEs
- All TE treatment-related SAEs
- All TEAEs leading to premature discontinuation of study drug
- All TEAEs leading to premature discontinuation of study
- All AEs leading to death (ie, outcome of death)

A brief, high-level summary of AEs described above will be provided by treatment group and by the number and percentage of subjects who experienced the above AEs. All deaths observed in the study will be also included in this summary.

Multiple events will be counted only once per subject in each summary. Adverse events will be summarized and listed first in alphabetic order of SOC and HLT within each SOC (if applicable), and then by PT in descending order of total frequency within each SOC. For summaries by severity grade, the most severe grade will be used for those AEs that occurred more than once in an individual subject during the study.

In addition to the above summary tables, all TEAEs and TE treatment-related AEs will be summarized by PT only, in descending order of total frequency.

In addition, data listings will be provided for the following:

- All AEs, indicating whether the event is treatment emergent
- All AEs of Grade 3 or higher
- All AEs of Grade 2 or higher
- SAEs
- Deaths
- All AEs leading to death (ie, outcome of death)
- AEs leading to premature discontinuation of study drug
- AEs leading to premature discontinuation of study

7.1.7. Additional Analysis of Adverse Events

Summaries (number and percentage of subjects) of AEs (by SOC and PT) will be provided by treatment group using the safety analysis set for the age, gender, and race subgroups.

Summaries (number and percentage) of subjects who experienced any cardiac related events will be provided for each treatment group using the Safety Analysis Set by AE of interest categories and the associated PTs (see Appendix 2).

7.2. Laboratory Evaluations

Laboratory data collected during the study will be analyzed and summarized using both quantitative and qualitative methods. Summaries of laboratory data will be provided for the Safety Analysis Set and will include data through Day 28. The analysis will be based on values reported in conventional units. When values are below the limit of quantitation, they will be listed as such, and the closest imputed value will be used for the purpose of calculating summary statistics. Hemolyzed test results will not be included in the analysis, but they will be listed in by-subject laboratory listings.

A by-subject listing for laboratory test results will be provided by subject ID number and visit in chronological order for hematology, serum chemistry, and urinalysis separately. Values falling outside of the relevant reference range and/or having a severity grade of 1 or higher on the Gilead Grading Scale for Severity of Adverse Events and Laboratory Abnormalities will be flagged in the data listings, as appropriate.

No inferential statistics will be generated.

7.2.1. Summaries of Numeric Laboratory Results

Descriptive statistics (sample size, mean, SD, median, Q1, Q3, minimum, and maximum) will be provided by treatment group for each laboratory test specified in the study protocol as follows:

- Baseline values
- Values at each post baseline assessment
- Change from baseline at each post baseline assessment

A baseline laboratory value will be defined as the last measurement obtained on or prior to the date/time of first dose of study drug. Change from baseline to a post baseline visit will be defined as the visit value minus the baseline value. Laboratory test results collected at unscheduled visits will be included for the baseline. The mean, median, Q1, Q3, minimum, and maximum will be displayed to the reported number of digits; SD to the reported number of digits plus 1.

Median (Q1, Q3) of the observed values for these laboratory tests will be plotted using a line plot by treatment group and visit.

In the case of multiple values in an analysis window, data will be selected for analysis as described in Section 3.8.4.

7.2.1.1. Troponin

Troponin will be collected at the visits pre-specified in the protocol: Day 1, Day 17 and Day 28 (End of study). A shift table of troponin results at postbaseline visit including those obtained for the purposes of standard of care compared with baseline values will be presented by treatment group using the following categories: normal, abnormal, or missing. The number and percentage of subjects in each cross-classification group of the shift table will be presented. Subjects with a missing value at baseline or postbaseline will not be included in the denominator for percentage calculation. No formal statistical testing is planned.

If multiple troponin results exist for one visit due to multiple troponin assay tests performed, the results obtained from Troponin I test will be used for the analysis.

All troponin results, including those not required by the protocol (see protocol Section 6.11.9.2), will be presented in the subject listings.

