6.11.8. Electrocardiogram (ECG)

As part of safety testing, at Visit 2 (Day 1) a pre-dose 12-lead ECG will be performed on the institution's equipment. A 12-lead ECG will also be performed pre-dose at Visit 8 (Day 17) and anytime at Visit 10 (Day 28). ECG results should be verified before the subject leaves the clinical site in case further medical care is advised. ECG testing done for the purposes of patient care on the same day as a protocol-required test day may be used, provided the test is completed at the protocol-directed time. Any additional ECG measures obtained for the purposes of patient care also require collection.

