6.11.9.2. Clinical Data Collection for Cardiac Related Tests

Aside from the protocol-specified ECG and troponin collection, additional cardiac-related tests are not required for this study. However, throughout the study period (Baseline/Day 1 through Day 28/End of Study) if any cardiac-related testing is performed as part of standard clinical care, or as part of AE/SAE evaluation and/or follow-up, these results will be collected, including but not limited to the following:

- ECG tracings and reports of any ECG performed
- All troponin testing
- Other cardiac enzyme testing (eg, all CK, CK-MB, etc)
- Cardiac stress testing
- Echocardiographic imaging (resting and stress testing)
- Cardiac perfusions scans
- Cardiac MRIs
- Any additional procedure used to evaluate cardiac conditions

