7.5. Electrocardiogram Assessment

A 12-lead ECG will be performed at Visit 2 (Day 1), Visit 8 (Day 17), and Visit 10 (Day 28) and read by a certified cardiologist at a specialized central laboratory. Summaries of ECG assessments will be provided for the Safety Analysis Set

Number and percent of subjects with new ECG abnormalities at postbaseline visits including those assessments obtained for the purpose of standard of care will be summarize by treatments. Only subjects with baseline ECG assessments will be included in this analysis.

A shift table of the ECG assessment at each scheduled visit compared with baseline will be presented by treatment group using the following categories: normal, abnormal, or missing. The number and percentage of subjects in each cross-classification group of the shift table will be presented. Subjects with a missing value at baseline or postbaseline will not be included in the denominator for percentage calculation. No formal statistical testing is planned.

A by-subject listing for ECG assessments and ECG abnormalities will be provided by subject ID number and visit in chronological order.

No formal statistical testing is planned.

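### Troponin and ECG abnormality summaries mix scheduled with care-driven tests, so they could lean towards presatovir if it lowers LRTC; troponin has no clearly scheduled-only table as a check

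*SAP*

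**What the plan says.** **Troponin.** SAP 7.2.1.1 names a baseline test and two scheduled post-baseline tests (Days 17 and 28). It then plans a shift table (normal, abnormal, missing) of "troponin results at postbaseline visit including those obtained for the purposes of standard of care compared with baseline values". Subjects without a baseline or a post-baseline value are left out of the percentages. Table 15.11.6.6.1 is this shift table. Table 15.11.6.6.2 reads as a count of subjects with an abnormal result at any point after baseline up to Day 28; its title does not say whether care tests are included.

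**ECG.** SAP 7.5 uses the same three days and plans two summaries. Table 15.11.9.2 covers "new ECG abnormalities at postbaseline visits including those assessments obtained for the purpose of standard of care". Table 15.11.9.1 is not pooled: "A shift table of the ECG assessment at each scheduled visit compared with baseline will be presented by treatment group".

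**Where the extra tests come from.** Protocol 6.11.9.2 says that "if any cardiac-related testing is performed as part of standard clinical care, or as part of AE/SAE evaluation and/or follow-up, these results will be collected", and its list includes all troponin tests and ECGs. Protocol 6.11.8 adds, for ECG: "Any additional ECG measures obtained for the purposes of patient care also require collection". Protocol 6.11.9.1 puts ECG reports linked to a possible LRTC among the material for adjudication. Protocol 8.10 has the adjudicators exclude heart failure and other non-respiratory causes.

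Neither SAP section plans to report how many tests were done in each arm.

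**The concern.** The chance that a subject is ever recorded as abnormal rises with the number of tests, even when the risk per test is the same. Here the number of tests is not fixed by design. Everyone is due two post-baseline tests, and the rest follow clinical events after randomisation. One of those events, LRTC, is a co-primary endpoint that presatovir is meant to reduce. If it does, and if LRTC prompts cardiac work-up, placebo subjects have more occasions to be found abnormal. A pooled comparison then mixes any effect of the drug on the heart with the effect of unequal testing, and the second favours presatovir. For ECG, the reader can turn to the scheduled-visit shift table. For troponin, the plan offers no table that is clearly limited to scheduled tests.

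**Working it through.** **1. The planned LRTC difference.** SAP 1.3 and Protocol 8.8 give 30% LRTC on placebo, a 20% reduction, 100 subjects per arm, a 2-sided level of 0.04 and power over 90%. With p1 = 0.30, p2 = 0.10 and mean 0.20:

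power = Φ{[0.20 × √100 − 2.054 × √(2 × 0.20 × 0.80)] / √(0.30 × 0.70 + 0.10 × 0.90)} = Φ(1.53) = 93.7%.

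This agrees with the plan. Reading the reduction as relative (30% to 24%) gives only 13.6%. The planned contrast is therefore 30% against 10%.

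**2. Model for an any-time count.** Each subject has two scheduled tests, each abnormal with probability s. A subject with LRTC has m further care tests, each abnormal with probability q. Tests are taken as independent.

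- No LRTC: P(ever abnormal) = 1 − (1 − s)²
- LRTC: P(ever abnormal) = 1 − (1 − s)²(1 − q)^m
- Placebo weights 0.70 and 0.30; presatovir weights 0.90 and 0.10

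The values of s, q and m are assumptions. The documents supply none of them.

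**3. No cardiac drug effect, s = 10%, m = 3.** Without LRTC: 1 − 0.9² = 19.0%.

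- q = 10%: with LRTC, 1 − 0.9⁵ = 41.0%. Placebo 0.70 × 19.0 + 0.30 × 41.0 = 25.6%; presatovir 0.90 × 19.0 + 0.10 × 41.0 = 21.2%. Difference −4.4 points.
- q = 20%: with LRTC, 1 − 0.81 × 0.512 = 58.5%. Placebo 30.9%; presatovir 23.0%. Difference −7.9 points.

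Using scheduled tests only, both arms are at 19.0% and the difference is 0. Across s = q from 5% to 15% and m from 1 to 4, the spurious difference runs from −0.9 to −6.9 points.

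**4. With a true cardiac effect, q = s within each arm** (differences in points, presatovir minus placebo):

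| Abnormal per test, placebo to presatovir | Scheduled only | Pooled, m = 1 | Pooled, m = 4 |
|---|---|---|---|
| 5% to 6% | +1.9 | +1.1 | −1.2 |
| 5% to 7.5% | +4.7 | +4.0 | +2.0 |
| 5% to 10% | +9.25 | +8.7 | +7.0 |

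If care tests during LRTC are instead abnormal 15% to 30% of the time in both arms (m = 1 or 2), the middle row ranges from +1.9 to −4.8 and the bottom row from +6.4 to −0.4.

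**5. If LRTC does not differ between arms** (10% or 30% in both, m = 1 or 2, q = s), the pooled difference for 5% to 10% is +9.6 to +11.2. Nothing is masked.

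**6. What the model covers.** It describes an ever-abnormal count. That fits Table 15.11.9.2, and Table 15.11.6.6.2 if care tests enter it. It does not describe a shift table that takes one record per subject and visit.

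**The case against.** The strongest reply is that the troponin wording may be narrower than it looks. Protocol 6.11.6 lets a patient-care troponin taken on a protocol test day, at the required time, stand in for the protocol test. SAP 3.8.3 keeps unscheduled visits out of by-visit summaries, and SAP 3.8.4 picks the record closest to the nominal day. SAP 7.2.1.1 states no worst-value rule and sends all troponin results to the listings. On that reading the troponin shift table is already close to scheduled-only. This stands in part: the step 3 figures must not be read as the bias in that table. But 7.2.1.1 does not cite 3.8.3, and where 7.5 limits the ECG shift table to scheduled visits, 7.2.1.1 expressly brings in care results. The selection rule is left open.

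Other points on that side also stand:

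- ECG is largely covered by Table 15.11.9.1.
- The documents tie ECGs, but not troponin tests, to LRTC work-up.
- Care tests also follow adverse events. If presatovir caused cardiac events, that route would add tests on presatovir and push the other way.
- A scheduled-only comparison has its own outcome-dependent gap. Its first test is on Day 17, so it misses earlier events and omits subjects who died or withdrew before then.
- The tables are descriptive. The troponin and ECG listings, the cardiac adverse event summaries (Tables 15.11.2.4 and 15.11.4.4) and the data monitoring committee's safety reviews all remain.

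A reader might also infer from the SAP revision log that these tables answer the regulator's cardiac monitoring requirement. The log gives that reason for Section 7.1.7 (cardiac adverse events of interest). For 7.2.1.1 and 7.5 it cites only detail and clarification.

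**Conclusion.** The pooling is in the text, and the number of care-driven tests depends on events after randomisation. If LRTC prompts cardiac testing and presatovir lowers LRTC, any-time abnormality counts could lean towards presatovir and dilute a small or moderate signal. With equal per-test rates, the illustrations put the lean at about 1 to 7 points. The true size is unknown: it rests on assumed test counts, assumed abnormality rates, independence between tests and the planned 30% against 10% LRTC.

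A reader might infer that an effective drug would hide its own cardiac harm. The documents do not support that. A large harm stays visible when care tests are abnormal at the same rate as scheduled ones, no masking appears when LRTC is equal, and other cardiac safety outputs remain. Nor do they show that placebo subjects will in fact be tested more.

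The point matters mainly for troponin. It is a cheap improvement of modest importance.

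**What to change.** Keep the pooled tables and add to them:

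- a troponin shift table by scheduled visit (Days 17 and 28), matching Table 15.11.9.1 for ECG;
- in Tables 15.11.6.6.2 and 15.11.9.2, separate rows for subjects abnormal on a scheduled test and subjects abnormal only on a standard-of-care test;
- the number of subjects tested and the number of tests per subject, by arm;
- a sentence in SAP 7.2.1.1 saying which result enters the troponin shift table when there are several, and how this fits the rule on unscheduled visits in SAP 3.8.3.

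The protocol already requires these data to be collected, so the cost is a change to table shells and a few more rows. Because the scheduled-only rows miss events before Day 17 and omit subjects who died or withdrew before then, they should supplement the pooled counts, not replace them.

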7.2.2. Graded Laboratory Values

The criteria specified in the study protocol will be used to grade laboratory results as Grade 0, mild (Grade 1), moderate (Grade 2), severe (Grade 3), or potentially life threatening (Grade 4). Grade 0 includes all values that do not meet criteria for an abnormality of at least Grade 1. Some laboratory tests have criteria for both increased and decreased levels; analyses for each direction (ie, increased, decreased) will be presented separately.

7.2.2.1. Treatment-Emergent Laboratory Abnormalities

Treatment-emergent laboratory abnormalities are defined as values that increase at least 1 toxicity grade from baseline at any post baseline time point, up to and including Day 28 visit. If the relevant baseline laboratory value is missing, then any abnormality of at least Grade 1 observed within the time frame specified above will be considered treatment emergent.

7.2.2.2. Treatment-Emergent Marked Laboratory Abnormalities

Treatment-emergent marked laboratory abnormalities are defined as values that increase from baseline by at least 3 toxicity grades at any post baseline time point, up to and including Day 28. If the relevant baseline laboratory value is missing, then any Grade 3 or 4 values observed within the timeframe specified above will be considered treatment-emergent marked abnormalities.

7.2.2.3. Summaries of Laboratory Abnormalities

The following summaries (number and percentage of subjects) of laboratory abnormalities will be provided by treatment group (subjects categorized according to most severe abnormality grade):

- Treatment-emergent Graded laboratory abnormalities
- Treatment-emergent Grade 3 or 4 laboratory abnormalities
- Treatment-emergent marked laboratory abnormalities

For all summaries of laboratory abnormalities, the denominator is the number of subjects with non-missing post-baseline values in the given study period.

A by-subject listing of treatment-emergent Grade 3 or 4 laboratory abnormalities and marked laboratory abnormalities will be provided by subject ID number and visit in chronological order. This listing will include all test results that were collected throughout the study for the lab test of interest, with all applicable severity grades displayed.

7.2.3. Liver-related Laboratory Evaluations

Liver-related abnormalities after initial study drug dosing will be examined and summarized using the number and percentage of subjects who were reported to have the following laboratory test values for post-baseline measurements:

- Aspartate aminotransferase (AST): (a) > 3 times of the upper limit of reference range (ULN); (b) > 5 x ULN; (c) > 10 x ULN; (d) > 20 x ULN
- Alanine aminotransferase (ALT): (a) > 3 x ULN; (b) > 5 x ULN; (c) > 10 x ULN; (d) > 20 x ULN
- AST or ALT: (a) > 3 x ULN; (b) > 5 x ULN; (c) > 10 x ULN; (d) > 20 x ULN
- Total bilirubin: (a) > 1 x ULN (b) > 2 x ULN
- Alkaline phosphatase (ALP) > 1.5 x ULN
- AST or ALT > 3 x ULN and total bilirubin: (a) > 1.5 x ULN; (b) > 2 x ULN
- AST or ALT > 3 x ULN, total bilirubin > 2 x ULN and ALP < 2 x ULN

The summary will include data from all post-baseline visits up to and including Day 28. For individual laboratory tests, subjects will be counted once based on the most severe post-baseline values. For both the composite endpoint of AST or ALT and total bilirubin, subjects will be counted once when the criteria are met at the same post-baseline visit date. The denominator is the number of subjects in the Safety Analysis Set who have nonmissing post-baseline values of all relevant tests at the same post-baseline visit date. A listing of subjects who met at least 1 of the above criteria will be provided.

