No subject experienced a serious AE. All AEs were mild or moderate (Grade 1 or 2) in severity, except for three Grade 3 AEs experienced by 1 placebo-treated subject (increased blood lactate dehydrogenase, alanine aminotransferase [ALT], and aspartate aminotransferase [AST]). Grade 1 pulmonary function decrease (<10% change) was the only treatment-related AE experienced by >2 subjects in either treatment group (presatovir: 4.6%, $n = 4/87$; placebo: 3.8%, $n = 2/53$). Changes in clinical laboratory values were Grade 1 or 2 in severity, except for one Grade 4 value

(increased AST; reported for placebo-treated subject described above). Elevated ALT was more commonly reported among presatovir-treated subjects (presatovir: 14.9%; placebo: 9.4%), but elevated AST was less commonly reported (presatovir: 5.7%; placebo: 15.1%). Low neutrophil count was reported as Grade 1 in 11 subjects (2 received placebo) and Grade 2 in 2 subjects (1 received placebo). Among the 9 subjects who experienced a Grade 1 low neutrophil count and received presatovir, 2 had a Grade 1 low neutrophil count at Screening. Clinically relevant changes in vital signs or ECGs were not observed.

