3.5. Discontinuation Criteria

Reasons for potential premature discontinuation from IMP dosing include:

- Any Grade 3 or 4 AE or SAE
- Intercurrent illness that would, in the judgment of the investigator, affect the subject's ability to receive IMP (eg, unable to ingest oral dose)
- ALT, AST $> 5 \times$ ULN and rising
- ALT, AST remains $> 5 \times$ ULN with no change in TB for more than 2 weeks
- A worsening of clinical symptoms with no other acceptable explanation
- Hy's Law criteria are met:
 - Evidence of injury: elevation of the ALT or AST by $> 3 \times$ ULN; and
 - Evidence of dysfunction: elevation of the TB by $> 2 \times$ ULN without an elevation of the alkaline phosphatase (ALP) by $> 2 \times$ ULN; and
 - Clinical verification to ensure effect is health product-induced and not induced by disease or another cause of injury

In the event that any of the above criteria are met, the Principal Investigator (PI) will review the case in detail and discuss with the Gilead Medical Monitor whether the subject should be discontinued from IMP. If close monitoring of ALT, AST, ALP, and TB per Section 6.11.6 is not possible, IMP will be discontinued.

Reasons for premature discontinuation from the Study include:

- Subject request to discontinue for any reason
- Subject noncompliance
- Pregnancy during the study; refer to Section 7.7.2
- Discontinuation of the study at the request of Gilead, a regulatory agency or an institutional review board or independent ethics committee (IRB/IEC)

If a subject prematurely discontinues from IMP dosing, he/she will remain on study and will continue with all subsequent Study Visits and assessments, with the exception of IMP dosing.

If a subject prematurely discontinues from the study, every attempt should be made to bring the subject back for the Early Termination procedures. See Section 6.9.2 for more information.

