7.7. Changes From Protocol-Specified Safety Analyses

No changes from protocol-specified safety analyses.

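### The SAP's same-date rule can leave a potential biochemical Hy's-law case out of the by-arm combined ALT/AST-and-bilirubin counts, although the case stays visible elsewhere

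*SAP*

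**What the plan says.** SAP 7.2.3 (Table 15.11.6.5) has two kinds of liver row.

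- **Single-test rows** for AST, ALT, AST or ALT, TB and ALP: "For individual laboratory tests, subjects will be counted once based on the most severe post-baseline values". The date does not matter.
- **Combined rows**: AST or ALT above 3 x ULN with TB above 1.5 or above 2 x ULN, and a three-test row, "AST or ALT > 3 x ULN, total bilirubin > 2 x ULN and ALP < 2 x ULN". The counting sentence opens "For both the composite endpoint of AST or ALT and total bilirubin" and goes on to say that "subjects will be counted once when the criteria are met at the same post-baseline visit date". The denominator requires "nonmissing post-baseline values of all relevant tests at the same post-baseline visit date".

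A by-subject listing covers anyone who meets at least one of the criteria.

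Protocol 3.5 gives Hy's law as one of several reasons to consider stopping study drug. It has three parts. The first is ALT or AST above 3 x ULN. The second is worded "Evidence of dysfunction: elevation of the TB by" more than 2 x ULN, without ALP raised above 2 x ULN. The third is clinical verification that the effect is due to the product. No part states a date or a time window.

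**The concern.** The SAP adds a concurrency condition that the laboratory elements of the protocol rule do not carry, and gives no reason for it. If bilirubin lags behind the transaminases, the two elevations may never appear on one date. An investigator could then review a subject under Protocol 3.5 while the combined rows for that arm show no such subject, and no stated rule reconciles the two outputs.

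The by-arm combined count is where a reader looks first for a liver signal. The SAP revision table says that this section was added to meet regulatory requirements, so its rows should be defined exactly. A listing is not a count by arm.

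**Working it through.** The plan gives no figure to reproduce here. The check sets the two rules side by side and applies them to illustrative profiles.

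**Inputs from the documents**

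- SAP same-date rule: some date with A > 3 and T > 2; for the three-test row, also P < 2. A is ALT or AST, T is TB and P is ALP, all in multiples of ULN.
- Protocol 3.5 laboratory parts, read without timing: A > 3 at some draw, and T > 2 at some draw with P not above 2. Clinical verification is a further step that a laboratory table cannot supply.
- Protocol 6.11.6: AST, ALT, ALP and TB are drawn together on Days 5, 9, 13, 17, 22 and 28 (six post-baseline dates). If ALT or AST exceeds 3 x ULN, or TB exceeds 2 x ULN, all four are repeated within 48 to 72 hours.

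**Profiles (assumed values, shown as A / T / P)**

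| | Draws | SAP two-test row, T > 2 | SAP three-test row | Protocol laboratory parts, untimed |
|---|---|---|---|---|
| A | Day 9: 4 / 2.5 / 1.2 | yes | yes | yes |
| B | Day 9: 4 / 1.2 / 1.2; Day 13: 2.6 / 2.5 / 1.2 | no | no | yes |
| C | Day 9: 6 / 1.2 / 1.2; Day 13: 3.5 / 2.5 / 1.2 | yes | yes | yes |
| D | Day 9: 4 / 2.5 / 2.0 | yes | no | yes |
| E | Day 5: 4 / 1.5 / 1.5; Day 9: 4 / 2.5 / 2.3 | yes | no | no |

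All five enter the single-test rows for A > 3 and T > 2, and all five are listed.

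- B is the gap: the elevations do not overlap at any draw.
- C shows that a lag alone loses nothing if A is still above 3 when T passes 2.
- D shows a separate mismatch. At P of exactly 2.0 the SAP row fails (below 2 is required), but the protocol part holds (not above 2). The SAP's counting sentence names AST/ALT and TB but not ALP, so the date at which ALP is judged is implied rather than stated.

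**Direction.** Any subject with A > 3 and T > 2 on one date also has maximum A > 3 and maximum T > 2. In each arm the any-time count is therefore at least the same-date count. The same-date rule can lower the count and never raise it.

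**Effect of the retest.** Suppose the Day 9 elevation is repeated at 48 or 72 hours and values move evenly from Day 9 to Day 13 (96 hours), so the fractions of the interval are 0.5 and 0.75.

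- Larger rise, Day 9 A 8 and T 1.6, Day 13 A 2.8 and T 3, ALP normal. On a linear path, 48 h gives A = 8 - 0.5 x 5.2 = 5.4 and T = 1.6 + 0.5 x 1.4 = 2.3; 72 h gives A = 4.1 and T = 2.65. On a log-linear path the values are 4.7 and 2.2, then 3.6 and 2.6. Every retest is concurrent, so this case is caught if retest dates count.
- Profile B. On a linear path, 48 h gives A = 4 - 0.5 x 1.4 = 3.3 and T = 1.2 + 0.5 x 1.3 = 1.85; 72 h gives A = 2.95 and T = 2.175. Neither is concurrent. Only a draw between about 59 h (0.8/1.3 x 96) and 69 h (1/1.4 x 96) would catch it. On a log-linear path, A falls to 3 at fraction ln(0.75)/ln(0.65) = 0.67, before T reaches 2 at ln(2/1.2)/ln(2.5/1.2) = 0.70, so no draw would.

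The retest thus closes the gap for large rises but not always for small ones.

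**Do retests count?** SAP 7.2.3 refers to all post-baseline visits. SAP 3.8.3 keeps unscheduled visits out of by-visit summaries, which this table is not. SAP 7.2.1 mentions unscheduled laboratory results only for baseline. The likely answer is yes, but it is not written.

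**Size of one case.** 189 enrolled / 2 is about 95 per arm, and 1/95 = 1.1%.

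**The case against.** The case for leaving the SAP alone is substantial, and much of it stands.

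- **Cases do not vanish from the liver table.** A reader might infer that they do. The single-test rows and the listing show every such subject. A laboratory abnormality that leads to stopping study drug must also be recorded as an adverse event (Protocol 7.1.3).
- **The SAP does not contradict the protocol.** Protocol 3.5 triggers a case review. It is not a table definition, it needs clinical verification, and it is silent on timing rather than stating that non-concurrent values qualify. Nor is the three-test row labelled Hy's law. Protocol 8.6.3 specifies no combined liver table, so SAP 7.7's statement, "No changes from protocol-specified safety analyses", is not made false by this rule.
- **The denominator rule has almost no effect.** The four tests are drawn together, and one complete date qualifies a subject.
- **Bias in favour of presatovir is not shown.** The rule is the same in both arms. The challenge study in Protocol 1.2.4.3 does not settle the matter: elevated ALT was more common on presatovir (14.9% against 9.4%), but elevated AST was less common (5.7% against 15.1%). Nothing in the documents supports a claim that one case would change the trial's conclusion.
- **Pairing maxima from any dates loses specificity.** Eligibility sets no numeric limit on ALT, AST or TB, so unrelated rises can be paired.

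What remains is narrow. Non-overlapping elevations are left out of the by-arm combined counts above 2 x ULN, and the SAP leaves the handling of retests and ALP unstated.

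**Conclusion.** The point holds in limited form. The same-date condition is in the SAP, the laboratory elements of Protocol 3.5 have none, and a subject such as profile B is absent from both combined rows above 2 x ULN. Against an any-time rule, the combined count can only be lower.

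The number affected cannot be derived, because the documents give neither the frequency of such elevations nor how often bilirubin lags. It is probably small given the joint panels and the 48-to-72-hour repeats. The profiles and the interpolation are assumptions that show how the rule works; they are not estimates. The defect is a less sensitive by-arm screen and an incomplete definition, not concealed cases. It deserves a cheap improvement.

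**What to change.** In SAP 7.2.3 and Table 15.11.6.5:

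1. Keep the same-date rows.
2. Add a supplementary row based on each subject's maximum post-baseline ALT or AST (above 3 x ULN) and maximum TB (above 2 x ULN) at any time through Day 28.
3. State that the 48-to-72-hour retests and unscheduled samples are included.
4. Show the dates of both peaks in the listing.
5. Reconcile the ALP criterion with Protocol 3.5. The two differ at exactly 2 x ULN, and the protocol attaches ALP to the TB elevation whereas the SAP does not say which draw applies. State the draw explicitly.

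This concerns the table only and leaves the protocol's discontinuation rule untouched. It uses data already collected and costs some SAP wording, one table row and listing columns. If the SAP is already final, its introduction provides for recording the change in the study report. The downside is that some unrelated, non-concurrent rises will be flagged in this population. The placebo arm and the listed dates let readers judge them.
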